10.2.3 Treatment-Emergent Adverse Events by SOC and/or PT

Treatment-emergent adverse events will be summarized for each of the following AE categories:

- TEAEs by SOC and PT
 - Ocular TEAEs by SOC and PT
 - Nonocular TEAEs by SOC and PT
- TEAEs by PT
- TEAEs with reasonable possibility of being related to study treatment by SOC and PT
 - Ocular TEAEs with reasonable possibility of being related to study treatment by SOC and PT
 - Nonocular TEAEs with reasonable possibility of being related to study treatment by SOC and PT
- TEAEs by SOC, PT, and maximum severity

Specific adverse events will be counted once for each subject for calculating percentages, unless stated otherwise.

If the same adverse event occurs multiple times for a subject, the highest severity and level of relationship to investigational product will be reported.

10.2.4 SAEs (Including Deaths) and Adverse Events Leading to Study Treatment Discontinuation

SAEs (including deaths) and AEs leading to study treatment discontinuation will be summarized by SOC and PT and in listing format.

10.2.5 Adverse Events of Special Interest

Adverse events of special interest in the following categories will be based on the search criteria in Appendix B:

- Headache AESIs
- Visual disturbance AESIs

The following treatment-emergent AESIs will be summarized overall and by PT:

- Headache AESIs
 - Headache AESIs with reasonable possibility of being related to study treatment
 - Headache AESIs with no reasonable possibility of being related to study treatment
- Visual disturbance AESIs

For each of the above categories of AESIs, descriptive summaries will be presented by treatment group for the following parameters:

- Any AESI
- Severity (mild, moderate, severe)

- Duration (days)
- Duration category (1 day, 2 to 5 days, 6 to 20 days, > 20 days)
- Onset day category (Day 1, Day 2 to Day 10, > Day 10)
- Pattern (continuous, intermittent)
- Outcome (recovered/resolved, recovered/resolved with sequelae, not recovered/not resolved, fatal, unknown)
- Concomitant medication or therapy (yes, no)
 - Yes, Outcome (recovered/resolved, recovered/resolved with sequelae, not recovered/not resolved, fatal, unknown)
 - No, Outcome (recovered/resolved, recovered/resolved with sequelae, not recovered/not resolved, fatal, unknown)
- Discontinuation from the study treatment
- Ongoing at exit

In addition, concomitant medications or therapy started on or after the first study treatment date for the indication of headache AESIs will be summarized by preferred drug name and by treatment group.

The following listings will be provided:

- Headache AESIs: with reasonable possibility of being related to study treatment
- Headache AESIs: with no reasonable possibility of being related to study treatment
- Visual disturbance AESIs.

10.2.6 Headache Assessment

Whenever a headache AE is reported after the initial dosing at Day 1, the subject will be followed up with a supplemental headache assessment form to further assess the headache. Severity score will be assessed using a visual analog scale (VAS) (0 – 100 for No pain – Worst possible pain):

- Overall headache/migraine severity score (0 – 100)
- Temporal headache/browache severity score (0 – 100)
- Supraorbital headache/browache severity score (0 – 100)

The number and percentage of subjects who had any of the above 3 VAS assessments will be summarized by treatment group for overall/temporal/supraorbital, respectively. In addition, the total number of assessments of overall headache/migraine, temporal headache/browaches, and supraorbital headache/browache will be summarized by treatment group.

In addition to the severity scores, the following information will be assessed for overall headache/migraine:

- Onset after the first or second dose of study medication (after first dose, after second dose, both, unsure)
- Intermittent status (yes, no)
- Onset time after taking the study medication (0-1 hour, > 1-2 hours, > 2-4 hours, > 4-6 hours, > 6 hours)
- How long did the headache/migraine last? (0-1 hour, > 1-2 hours, > 2-4 hours, > 4-6 hours, > 6 hours)

All headache assessments for TEAEs will be summarized using descriptive statistics by treatment group. The percentages will be based on the total number of assessed events by treatment group, whenever applicable. For intermittent status, only the category of "Yes" will be summarized.

Additionally, similar summaries will be provided for the following 2 subsets:

- Supplemental headache assessments for TEAEs with reasonable possibility of being related to study treatment
- Supplemental headache assessments for TEAEs with no reasonable possibility of being related to study treatment

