The evaluator should also ask the subject the additional questions on the headache AE-assessment form. If a headache started after administration of both the first and second doses of study drug, then these additional questions should be answered about whichever headache had worse outcomes. For example, "How long after taking the study drug did the headache/migraine start?" should reflect whichever headache had the quickest onset, and "How long did the headache/migraine last? (if intermittent, approximately how long did each event last)" should reflect whichever headache had the longest duration.

The evaluator should measure the distance from the end of the line to the mark that the subject made with a ruler and record the length on the supplemental headache assessment worksheet.

If a headache is classified as intermittent or recurrent with the same causality and severity, then one supplemental headache AE assessment form should be used. If the subject experiences multiple headaches with different causality or severity, then each headache should have its own supplemental headache AE assessment form.

COVID-19 Pandemic-Related Acceptable Protocol Modifications

Supplemental study CRFs should be completed in the event of COVID-19-related missed/virtual visits, study drug interruptions or discontinuations, or AEs (including capture of specific signs/symptoms of infection and testing results).

Severe acute respiratory syndrome coronavirus 2 (SARS-CoV-2) infections should be captured as AEs. If the event meets the criteria for a SAE, then follow the SAE reporting directions per the protocol and above. The following COVID-19-related supplemental eCRFs should be completed (for both serious and nonserious events):

- COVID-19 Supplemental Signs/Symptoms
- COVID-19 Status Form

If a subject has a confirmed or suspected SARS-CoV-2 infection and study drug was interrupted, the investigator should contact the sponsor emergency medical contact listed above before reintroducing study drug.

Reactions known to be associated with the SARS-CoV-2 vaccine should be reported as AEs. If the event meets the criteria for an SAE, then follow the SAE reporting directions. All AEs associated with the SARS-CoV-2 vaccine will be linked to the vaccine on the COVID-19 Vaccine eCRF.

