10.5.7 Post-Dose Tolerability

Post-dose tolerability will be assessed after each dose at each visit in all subjects who report any of the following ocular symptoms after drop instillation:

- blurred vision/vision disturbance
- foreign body sensation/grittiness
- pain
- burning/stinging/irritation
- tearing/watery eyes/discharge
- itching

These subjects will rate each of these symptoms using a 5-point scale (0 = none, 0.5 = trace, 1 = mild, 2 = moderate, and 3 = severe) for severity and a 3-point scale (< 1 min, 1 to 5 min, and > 5 min) for duration. The number and percentage of subjects who report each category of severity and duration will be tabulated for each time point by treatment group.

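### Headache VAS severity, onset and hours of duration are tabulated only per assessed event; no planned table gives VAS severity or hours per treated subject

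*SAP*

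**What the plan says.** SAP 10.2.6 takes its data from the supplemental headache form: three VAS scores (overall, temporal, supraorbital), whether onset followed the first or second dose, intermittent status, time to onset, and duration. Onset time and duration share five bands: 0–1, >1–2, >2–4, >4–6 and >6 hours. On analysis it says "All headache assessments for TEAEs will be summarized using descriptive statistics by treatment group" and "The percentages will be based on the total number of assessed events by treatment group, whenever applicable". It does not define an assessed event.

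The Operations Manual (Protocol Appendix F), Section 4.2, decides how many forms a subject produces. If a headache is classed as "intermittent or recurrent with the same causality and severity, then one supplemental headache AE assessment form should be used". Conversely, "If the subject experiences multiple headaches with different causality or severity, then each headache should have its own supplemental headache AE assessment form". Where headaches followed both doses, the additional questions describe the worse outcome: the quickest onset and the longest duration.

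Some subject-level output is planned. SAP 10.2.6 gives the number and percentage of subjects with each type of VAS assessment, and the total assessments per arm. SAP 10.2.3 counts each subject once per adverse event and adds a table by maximum severity. SAP 10.2.5 summarises headache events of special interest overall and by preferred term, including severity.

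**The concern.** Protocol 2.1 names temporal and periorbital headache as the effect that limits pilocarpine use, and Protocol 6.1 makes headache an adverse event of special interest. An acceptable safety and tolerability profile at twice-daily dosing is one of the stated clinical hypotheses (Protocol 3.1, SAP 2.1.2). A reader will want to know how bad the headaches were and how long they lasted, by arm.

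For VAS severity and hours of duration, the only planned answer is the event table. Its denominator arises after dosing and may differ greatly between arms, so it is not a denominator that randomisation makes comparable. Nor is it clearly a count of headaches, given the merging and splitting rules. At stake is how a descriptive safety table is interpreted, not any inferential result.

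**Working it through.** The plan states no figure for this table, so there is nothing to reproduce. The check is whether event percentages can differ from subject percentages, and in which direction. All headache counts below are assumptions. Only the 100 subjects per arm comes from the plan (SAP 2.4), and all 100 are taken as treated.

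**1. Event against subject denominator, headaches over 6 hours.** Assume each long form comes from a different subject.

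| | Active | Vehicle |
|---|---|---|
| Subjects with headache | 20 | 5 |
| Forms | 30 | 5 |
| Forms over 6 h | 6 | 2 |
| Per form | 6/30 = 20% | 2/5 = 40% |
| Per subject | 6/100 = 6% | 2/100 = 2% |

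The event table favours active; the subject table favours vehicle.

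**2. Fragility.** With one long vehicle form instead of two, the event table shows 20% against 1/5 = 20%, and the subject table 6% against 1/100 = 1%. One vehicle form is worth 1/5 = 20 percentage points. A second set of counts behaves the same way for headaches over 2 hours: 12/30 = 40% against 3/6 = 50% reverses, but 2/6 = 33% does not.

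**3. Splitting.** Suppose each affected subject has one long form and m extra short forms. The share of long forms is 1/(1 + m): 100%, 50%, 33% and 25% for m = 0, 1, 2 and 3. The number of affected subjects is unchanged. Protocol 6.1 adds to splitting, because worsening in severity is reported as a new adverse event.

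**4. Merging.** Four forms with one short headache each, plus one form covering ten long headaches, give 1/5 = 20% long by form and 10/14 = 71% by headache.

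**5. Worst-of recording.** If each headache has chance p of exceeding 6 hours, independently, a form covering two headaches shows 1 − (1 − p)². For p = 10%, 20% and 30% this is 19%, 36% and 51%. This makes the arm with more headaches look worse. One form may also pair the onset of one headache with the duration of another.

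**6. What the other tables cover.** In the example of step 1, SAP 10.2.6 itself would show 20% against 5% of subjects assessed and 30 against 5 assessments. SAP 10.2.3 and 10.2.5 add incidence and investigator-rated severity. None of them gives a VAS score or hours of duration with treated subjects as the base.

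**The case against.** The strongest reply is that this is a conventional event description beside adequate subject-level tables. The form is a headache adverse event form, and its rules resemble the adverse event convention, so an assessed event most naturally means a headache adverse event. Describing timing and duration given that an event occurred is a legitimate question. The reversal depends on invented counts, and the worst-of rule pushes against the arm with more headaches. Scoring 0 for a subject who never completed a VAS assigns an unmeasured value.

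Most of this stands. It limits the point to a missing table, an undefined unit and missing labels. It does not supply VAS severity or hours per treated subject. The 0 is defensible only where no headache adverse event was reported, and it should be footnoted as assigned.

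A reader might infer four stronger things that the documents do not support:

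- *That the plan conceals headache frequency or favours active.* Frequency is reported by subject, and the direction of distortion is not fixed.
- *That VAS scores could be reversed*, because "The evaluator should measure the distance from the end of the line to the mark that the subject made with a ruler" does not name the end. The same manual section puts no pain on the left and worst pain on the right, and SAP 10.2.6 defines 0–100 in that order.
- *That a short headache recurring over 14 days appears only as a 14-day event.* SAP 10.2.5 reports pattern as well as days. The manual asks how long each episode lasted if intermittent, and SAP 10.2.6 reports those hours.
- *That SAP 10.5.7 has the same fault*, because "These subjects will rate each of these symptoms using a 5-point scale" refers to symptomatic subjects. That section states no percentage denominator, so no defect is shown.

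**Conclusion.** The point holds in a limited form. The percentages in SAP 10.2.6 are conditional on an undefined event unit that depends on form merging and splitting. They should not be read as a comparison of randomised arms. The gap is specific: VAS severity and hours of headache are never shown per treated subject.

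The size cannot be estimated from the documents, which give no headache rates. The examples show that distortion is possible in both directions and that small vehicle counts make the percentages unstable; they do not predict what will be seen. The argument assumes that one assessed event corresponds to one form, which is a reasonable reading but not a stated one. The consequence is confined to descriptive safety reporting. The fix is worth making because it is cheap and headache is the tolerability question the protocol itself raises.

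**What to change.** In SAP 10.2.6:

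- Add a subject-level table by arm on the safety population: number and percentage of all treated subjects with any treatment-emergent headache lasting more than 2, 4 and 6 hours. These cut-points fall on existing band boundaries, and the longest-duration rule already supplies the value needed when headaches follow both doses.
- In the same table, give worst VAS per subject. Assign 0 only where no headache adverse event was reported; treat a headache adverse event without a form as missing, and show how many there are.
- Keep the event table as descriptive support. Define *assessed event* as form, adverse event or headache episode; label its percentages as conditional on an assessed event; and footnote the one-form and worst-of rules.

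Crossing duration in days with the continuous or intermittent pattern in SAP 10.2.5 is optional. No change to SAP 10.5.7 follows from this point.

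The cost is some SAP wording and one extra descriptive table from data already collected.

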10.3 Analysis of Laboratory Data

Urine pregnancy test will be performed at Screening, Day 1, and Day 14 for women of childbearing potential only.

10.4 Analysis of Vital Signs

Descriptive statistics for vital signs (systolic and diastolic blood pressure, and pulse rate) and changes from baseline values at each assessment timepoint will be presented by treatment group.

10.5 Other Safety Analyses

10.5.1 Mesopic, High-Contrast, Binocular CDVA

Mesopic, high-contrast, binocular CDVA is assessed at each visit.

Change from baseline in number of letters in mesopic, high-contrast, binocular CDVA will be summarized descriptively for each assessment timepoint by treatment group.

10.5.2 Photopic, High-Contrast, Binocular CDVA

Photopic, high-contrast, binocular CDVA is assessed at each visit.

Change from baseline in number of letters in photopic, high-contrast, binocular CDVA will be summarized descriptively for each assessment timepoint by treatment group.

10.5.3 Intraocular Pressure

IOP is measured for each eye using the Goldmann applanation tonometer at Hour 0, Hour 1, and Hour 7 (1 hour after the second dose) at each visit.

Tabulations will be based on the eye with a greater magnitude of change from baseline assessed at each assessment time point of a visit. In case of both eyes have same magnitude change in different directions, the decrease change from baseline will be

chosen. Descriptive statistics for IOP and changes from baseline at each assessment timepoint will be presented by treatment group.

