Pilocarpine ophthalmic solutions are currently used for the reduction of elevated intraocular pressure (IOP) in patients with open-angle glaucoma or ocular hypertension, management of acute angle-closure glaucoma, prevention of postoperative elevated IOP associated with laser surgery, and induction of miosis.⁹ Currently the use of pilocarpine ophthalmic solution is limited by the commonly experienced adverse event (AE) of temporal and periorbital headache (i.e., brow ache), which is believed to be due to the rapidity of the ciliary muscle contraction.¹⁰ However, AbbVie (formerly Allergan) has established an acceptable safety profile of AGN-190584 in 3 Phase 2 clinical studies (Studies 199201-007, 199201-009, and 199201-010) and 2 Phase 3 studies (1883-301-013 and 1883-302-013). This is likely because the posology of pilocarpine evaluated for the treatment of presbyopia to date is of lower concentration (0.5% to 1.5%) and less frequently administered (once to twice daily) than for the treatment of glaucoma (1.0% to 4.0% administered up to 4 times daily). As a result, discontinuation rates for all clinical studies were generally low and safety parameters were not clinically significant between subjects who received AGN-190584 compared to subjects who received vehicle or a combination therapy. The majority of AEs reported in any treatment group were mild to moderate in severity. More detailed information regarding clinical safety findings, clinical efficacy findings, chemistry, and pharmacology is provided in the Investigator's Brochure (IB).

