3.20 IOP

Intraocular pressure (IOP) should be measured after the biomicroscopic exam is completed and prior to pupil dilation. Measurements should be taken using a Goldmann applanation tonometer affixed to a slit-lamp with the participant seated. The participant and slit-lamp should be adjusted so that the participant's head is firmly positioned on the chin rest and against the forehead rest without leaning forward or straining. Tight fitting neckwear should be loosened. Both eyes will be tested, with the right eye preceding the left eye. The measurer will look through the binocular viewer of the slit lamp at low power. The tension knob will be preset at a low-pressure value (4 to 6 mm Hg). The measurer will follow the image of the fluorescein-stained semicircles while slowly rotating the tension knob until the inner borders of the fluorescein rings touch each other at the midpoint of their pulsation in response to the cardiac cycle. When this image is reached, the measurer will take his/her fingers off the tension knob and record the IOP reading along with the date and time of day.

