9.0 Efficacy Analyses

9.1 General Considerations

All efficacy analyses will be conducted for all efficacy endpoints in the ITT population at the end of the study and after the database has been locked. All tests will be 2-sided at an alpha level of 0.05. All confidence intervals (CIs) will be at least 2-sided 95% confidence.

Unless otherwise specified, the comparison of the proportions between AGN-190584 and vehicle will be made using the Pearson's chi-square test, and the treatment difference will be provided with a 2-sided 95% CI using the normal approximation based on the pooled variance without continuity correction.

Continuous variables will be analyzed using an analysis of covariance (ANCOVA) model that includes treatment, age group, baseline DCNVA severity group, iris color group, and emmetrope status as factors as well as corresponding baseline value as a covariate.

Unless otherwise specified, any mis-stratified subject will be analyzed based on the actual stratum the subject should have been randomized.

"Baseline" refers to the last non-missing observation before the first administration of study treatment or randomization if no study treatment is given. The change from baseline values will be computed as the postbaseline value minus the baseline value.

For descriptive analyses:

- Categorical variables will be summarized with the number and percentage of subjects; unless otherwise stated, percentages will be calculated based on the number of non-missing observations.
- Continuous variables will be summarized with descriptive statistics (number of nonmissing observations, mean and standard deviation, median, 1st and 3rd quartiles, minimum, and maximum).

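### The one-eye IOP summary exaggerates mean change in whichever direction prevails, and its tie-break always discards the rise, with no other planned IOP output to show it

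*SAP*

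**What the plan says.** SAP section 10.5.3 has IOP measured in each eye at Hours 0, 1 and 7 of each visit, and the Operations Manual (section 3.20) confirms the bilateral measurement: "Both eyes will be tested, with the right eye preceding the left eye". The summary then keeps one eye per subject and timepoint: "Tabulations will be based on the eye with a greater magnitude of change from baseline assessed at each assessment time point of a visit". For equal changes of opposite sign, "In case of both eyes have same magnitude change in different directions, the decrease change from baseline will be" chosen. The planned output is this: "Descriptive statistics for IOP and changes from baseline at each assessment timepoint will be presented by treatment group".

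Change is defined once, in SAP section 9.1: "The change from baseline values will be computed as the postbaseline value minus the baseline value". A positive change is therefore a rise in pressure. Protocol section 3.6 and SAP section 3.4 both list IOP among the safety measurements. Protocol section 2.1 gives the expected direction for the drug class: "Pilocarpine ophthalmic solutions are currently used for the reduction of elevated intraocular pressure (IOP) in patients with open-angle glaucoma or ocular hypertension".

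**The concern.** Two separate features of the rule matter.

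- **Selection on absolute change.** The reported mean is not the mean change of any eye. It is pushed away from zero and the SD is inflated. For a drug expected to lower pressure, the table would show more lowering than occurred.
- **The tie-break.** In a safety table the finding of interest is a rise. When the two eyes move equally in opposite directions, the rule always keeps the fall. The SAP gives no reason for this.

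Together they mean that a rise in one eye leaves the table whenever the fellow eye falls by the same amount or more. The SAP plans no per-eye IOP table, no count of subjects above a given rise and no IOP listing. By contrast, manifest refraction and fundus findings are listed (SAP 10.5.5 and 10.5.6). The slit-lamp rule (SAP 10.5.4) is directional and counts worsening in one or both eyes. The IOP rule has neither safeguard.

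**Working it through.** SAP section 10.5.3 states no figure to reproduce, so the check applies its rule to paired eye changes.

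**Rule.** Let R and L be the changes in the two eyes. The tabulated value T is the one with the larger absolute value. If R = -L (not zero), T is the negative one. Three cases:
- R = +3, L = -1: T = +3, and the rise is shown.
- R = +3, L = -3: T = -3, and the tie-break drops the rise.
- R = +3, L = -4: T = -4, and the selection rule drops the rise.

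**Inputs.** The rule and the sign of change come from SAP 10.5.3 and 9.1. The documents give no mean IOP change, SD or between-eye correlation, so these are assumed: true mean -1.0, 0 or +1.0 mmHg; per-eye SD of change 1.8 to 3.0 mmHg; correlation 0.4 to 0.9; changes rounded to whole mmHg. Two million subjects were simulated per setting.

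**Results for selected settings.** The last two columns take subjects with at least one eye rising by the stated amount, and give the share whose tabulated value does not show such a rise.

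| True mean | SD | Corr. | Tabulated mean | Mean with ties to increase | Rise ≥3 lost | Rise ≥5 lost |
|---|---|---|---|---|---|---|
| -1.0 | 3.0 | 0.4 | -1.50 | -1.31 | 9% | 1.2% |
| -1.0 | 3.0 | 0.7 | -1.32 | -1.20 | 1.5% | <0.1% |
| -1.0 | 1.8 | 0.9 | -1.15 | -1.12 | 0% | 0% |
| 0 | 3.0 | 0.4 | -0.10 | +0.10 | 6% | 0.6% |
| 0 | 1.8 | 0.9 | -0.02 | +0.02 | 0% | 0% |
| +1.0 | 3.0 | 0.4 | +1.31 | +1.50 | 3.5% | 0.3% |
| +1.0 | 1.8 | 0.9 | +1.12 | +1.15 | 0% | 0% |

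**Mean.** With a negative true mean, the lowering is overstated by about 0.15 to 0.50 mmHg. With a positive true mean of the same size, the rise is overstated by about 0.12 to 0.31. The two are not mirror images because the tie-break always acts downward. At a true mean of 0 only the tie-break acts, by about 0.02 to 0.10.

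**Tie-break alone.** The difference between the two mean columns is 2 × E[|R|; R = -L]. Examples: -1.31 - (-1.50) = 0.19; +0.10 - (-0.10) = 0.20; -1.12 - (-1.15) = 0.03. Equal and opposite changes make up roughly 2% to 8% of readings.

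**SD.** At a true mean of -1.0, the SD of T is about 10% to 22% above that of a single eye.

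**Between-group difference.** If the active group truly changed by -1.0 and vehicle by 0, the tabulated difference at SD 3.0 and correlation 0.4 is -1.50 - (-0.10) = -1.40. At SD 1.8 and correlation 0.9 it is -1.15 - (-0.02) = -1.13. Applying the same rule to both arms does not cancel the distortion.

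**Smaller rises.** At a true mean of -1.0, up to 19% of rises of 2 mmHg or more are lost. That is the setting with SD 3.0 and correlation 0.4; at correlation 0.8 the share is 0.4% to 3.5%.

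**The case against.** The strongest reply is that selecting the larger absolute change is symmetric. If IOP rose on average, which is the case a safety table exists to detect, the rule would magnify the rise. This stands. A reader might infer that the rule always overstates lowering or always errs in the reassuring direction, and the documents do not support that. Only the tie-break is one-sided, and it is worth about 0.2 mmHg at most. Nor do the documents state an expected IOP change in this population. Protocol section 2.1 describes use in elevated pressure, whereas section 5.1 excludes glaucoma and ocular hypertension. A fall is the likelier direction, but its size is unknown.

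A second reply is that few rises that matter are lost. This also largely stands. The larger losses need a high SD with a low between-eye correlation; at high correlation almost nothing of 3 mmHg or more disappears. A rise that the investigator judged an adverse event would still reach the adverse event tables (Protocol section 6.1, SAP section 10.2). That route depends on judgement, however, and does not replace a summary of the measurements.

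A third reply concerns the remedy. Replacing the rule with a two-eye average would mask more rises than the rule does. At a true mean of -1.0 and correlation 0.4 to 0.8, averaging brings 45% to 86% of subjects with a rise of 3 mmHg or more in at least one eye below 3, against 0% to 9% under the SAP rule. This is correct, so an average cannot be the fix by itself.

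**Conclusion.** The point holds in a limited form. The rule gives a biased estimate of mean IOP change in whichever direction prevails, and overstates lowering if IOP falls on average. The tie-break has no stated rationale and works against the safety signal. No planned IOP output recovers a rise that the rule discards.

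The sizes are modest and conditional on the assumed SD, correlation and mean. It would go too far to say that large pressure rises vanish from the report: at 5 mmHg or more the loss is about 1% or less in every setting examined. One descriptive safety table is affected; power, type I error and the efficacy results are not. The change is worth making because it is cheap and the measurements are already collected.

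**What to change.** Amend SAP section 10.5.3 as follows:

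1. If the one-eye rule is kept, resolve equal and opposite changes to the increase.
2. Add a table of the largest increase in either eye per subject and timepoint, by treatment group, with n (%) of subjects above increases fixed before unmasking. This table and the reversed tie-break carry the safety purpose.
3. Report mean change for OD and OS separately as the unbiased estimate. A two-eye mean is acceptable for this only alongside the largest-increase table.

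The cost is SAP wording and one or two tables from data already collected. No change to visits, procedures or sample size is needed.
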